CLL is considered incurable but treatable and the majority of recently diagnosed patients present with asymptomatic, early stage disease (Hallek et al., 2018b). In such cases the current gold standard approach is clinical observation without therapy – defined as 'watch and wait' - patients are monitored without anti-CLL treatment, until there is evidence of progressive or symptomatic disease, summarised and defined as 'active disease' (Hallek et al., 2018a). Patients with asymptomatic, early stage CLL, monitored via 'watch and wait', will be referred to as patients with 'watch and wait' CLL, throughout this protocol. Patients with 'watch and wait' CLL are reviewed at least twice within the first year from diagnosis to assess the rate of disease progression, for those with stable disease, monitoring is then extended to an annual check (Oscier et al., 2012). The purpose of disease monitoring is to identify progression to 'active disease' and commence active treatment, typically via chemoimmunotherapy, depending on the patient's clinical stage and symptoms. Current guidelines do not recommended treatment in 'watch and wait' CLL, clinical trials investigating early therapeutic intervention have not observed an improved clinical outcome in patients with CLL when compared to 'watch and wait' (Herling et al., 2020, Dighiero et al., 1998, Hoechstetter et al., 2017, Hallek et al., 2018a). Therefore, the evidence gained from clinical trials suggests that there is no clinical benefit of exposing patients with asymptomatic, early stage disease to the toxicity of anti-CLL treatment before there are signs of progression to 'active disease'. Moreover, the majority of patients with 'watch and wait' CLL experience an indolent disease course with neither compromising morbidity nor an elevated risk of premature death caused by the CLL (Binet et al., 1981). Therefore, people with 'watch and wait' CLL may benefit from non-toxic interventions that delay the progression to 'active disease'.

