This is a single-centre, double armed, randomised-controlled, phase I pilot trial, designed to evaluate the safety and acceptability of an incremental, multi-modal, 16-week exercise training intervention. The intervention will be observed by a member of the Research Team via a video communication platform in physically inactive people with 'watch and wait' CLL, compared to standard care, which comprises routine clinical monitoring.

Participant eligibility criteria

The following inclusion criteria define people who are eligible for the trial:

- Males and females with a working diagnosis of: Chronic lymphocytic leukaemia. Defined by iwCLL guidelines as the presence of 5000 B cells per µL of peripheral blood, sustained for at least 3 months and confirmed by the blood smear, immunophenotype and in some cases genetic features of lymphoid cells (Hallek et al., 2018a).
- Age > 18 years old.
- Asymptomatic early stage disease monitored without anti-CLL treatment.
- Physically inactive (defined by World Health Organisation as 'An insufficient physical activity level to meet present physical activity recommendations'. Current physical activity guidelines for adults are at least 150-300 minutes of moderate-intensity aerobic physical activity, or at least 75-150 minutes of vigorous-intensity aerobic physical activity, or an equivalent combination of both throughout the week (Bull et al., 2020)).
- Access to an appropriate electronic device (e.g. laptop, tablet or smart phone) with an appropriate wireless internet connection (and data allowance if relevant) capable of streaming video.
- All participants will have completed the full appropriate vaccination schedule including seasonal influenza, pneumococcal and COVID-19.

Sub-groups will be excluded due to safety risks:

- World Health Organisation (WHO)/ Eastern Cooperative Oncology Group (ECOG) performance status >1
- Pregnancy
- Deemed unsafe to exercise according to the Physical Activity Readiness Questionnaire (PARQ)
- Any comorbidity that is likely to progress or be exacerbated over the course of the trial period (e.g. history of syncopal events, significant cardiac or respiratory events)
- Cognitive impairment deemed a risk by the healthcare team for participation in the trial (e.g. diagnosis of neurodegenerative disease)
- Unable to understand explanations and/or provide informed consent
- Any condition and/or behaviour that would pose undue personal risk or introduce bias into the trial

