Safety: Incidence and severity of adverse events (Table 2). [Recording and reporting of SAEs will follow University of Bath policy – The chief investigator (CI) will report any SAE to the sponsor within 24 hours. A written SAE report (health research authority [HRA] form) will be made by the lead researcher and sent to the CI who will assess the seriousness, causality and expectedness. Where the SAE is related and unexpected, the CI will notify the research ethics committee (REC) within 15 days of receiving the report. AEs and SAEs will be discussed by the trial management group.]

Table 2: Definitions of adverse events

Definitions of adv	erse events
Term	Definition
Adverse Event (AE)	Any untoward medical occurrence in a participant to whom an intervention has been administered, including occurrences which are not necessarily caused by or related to that product.
Serious Adverse Event (SAE)	A serious adverse event in the context of this trial is any untoward medical occurrence that:
	results in death
	is life-threatening
	• requires inpatient hospitalisation or prolongation of existing hospitalisation
	 results in persistent or significant disability/incapacity
	Other 'important medical events' may also be considered serious if they jeopardise the participant or require an intervention to prevent one of the above consequences.
	NOTE: The term "life-threatening" in the definition of "serious" refers to an event in which the participant was at risk of death at the time of the event; it does not refer to an event which hypothetically might have caused death if it were more severe.

Visit 3 (Week 17)

Free-living measurements will be repeated post trial period (week 17). Resources and equipment (i.e. an instruction pack, food diary and physical activity monitor) to complete these measures will be sent to participants and can be returned during Visit 3.

After the trial period, participants will complete Visit 3, lasting 90-minutes. Measurements conducted during Visit 3 will replicate Visit 2, as described above.

Withdrawal criteria

Participants may be withdrawn from the trial if there is a change in their eligibility e.g. disease progression to 'active disease'. During Visit 2, contraindications and limitations to exercise may be identified during the exercise test (Ats and Accp, 2003) which will result in participants being withdrawn on safety grounds. All withdrawals will be discussed with the haematologist and reported in primary outcomes (retention).

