An unsupervised walking session has been included to increase exercise frequency without the additional burden of an observed session on participant's time. Home-based sessions have been selected to reduce the burden of travel and to reduce the COVID-19 risks for participants.

Exercise sessions

Exercise sessions will be performed in the participants home and will be observed by a member of the research team via the Microsoft Teams video communication platform. At the beginning of each trial week participants will be emailed the link to attend the observed exercise training sessions. Each session lasts approximately 1 hour, and equipment needed for all exercises will have been delivered to participants homes prior to the first session, including resistance bands, static exercise bikes (Matrix U1) and a blood pressure monitor. A brief screening, including blood pressure measurement and review of health status, will take place before each observed session to determine safety to exercise (unsafe if: blood pressure >200/120 mmHg (Ats and Accp, 2003) or participant reports new symptoms).

Exercise sessions will be offered at various times throughout the day, so the programme is accessible to as many participants as possible, including those with diverse/busy routines (e.g. working / retired). Each training session will have a small number of participants, all participants will be given the choice of whether they would like to see other members of the class on the screen at the same time, or not. There will be drop-in sessions available for participants who have not been able to attend their scheduled exercise sessions.

Aerobic component: Participants will perform a warm-up on the static bike at a comfortable cycling speed with no resistance ('unloaded cycling') for a minimum of 5 minutes. Aerobic training will then commence for 30 minutes. Participants will perform three sets of 10-minute cycling intervals (Table 3). For each interval, the resistance is increased during the 'work phase' to achieve a target work rate in watts (8 minutes, -5% - +15% of lactate threshold) followed by 'unloaded cycling' (2 minutes). Target work rate in watts will be prescribed using work rate data measured during the lactate threshold test; participants will be given a work rate zone in watts that corresponds to the target percentage of lactate threshold work rate.

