Instruction on how to perform behaviour	• The researcher will teach the participants how to perform the different exercises outlined in the exercise programme.
Social support	• Online group exercise sessions will create a social environment for related peers, with the aim to keep classes at consistent times for each participant to allow relationships to be formed within the group.
	• The researcher will encourage participants to identify a peer from their own social network to join them for the unsupervised walking sessions.

Action planning	•	The	exercise	programme	has	а	highly	structured,
		progressive action plan for 16 weeks.						

Control arm (CON) (for 16 weeks)

Control participants will not take part in an exercise training intervention, but will be offered exercise advice post-intervention (to minimise contamination of the control group).

Benefits of participating

Participants will be provided with feedback on some of their results within two months of their last visit. This will include blood pressure, body composition, cardiovascular fitness and physical capacity, with reference to the average population and recommended guidelines. Feedback will not be provided on data collected from blood samples because most of the measurements are preliminary research parameters and are not diagnostic.

Abnormal results from the exercise test will be shared and discussed with the haematologist, who may advise referral to another healthcare professional (e.g. general practitioner or cardiologist) which will be done by letter or email. In this case, 'abnormal' is defined as the presence of a criteria for exercise contraindication or early test termination, as defined in the guidelines (Ats and Accp, 2003).

Participants in the exercise training intervention group will receive 32 observed exercise sessions for free.

Participants in both groups will be given an information sheet upon completing the exercise programme with recommendations on staying active upon completion of this study. This will include a home-exercise programme and resistance bands provided free of charge, and information on local exercise referral schemes.

There is no financial compensation for visits to the University of Bath, but reasonable travel expenses will be reimbursed, and parking is free of charge.

Risks of participating

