The trial has been designed to reduce risks and burdens as much as possible, with the further aim of reducing potential risks and burdens further by strict adherence to best practice.

The exercise components of the trial (exercise tests and the exercise sessions) carry a risk of injury and acute complications.

- The acute risks of exercise will be minimised by performing thorough screening at trial entry via medical note review by the haematologist, PARQ, blood pressure checks, and resting ECG.
- Risk will also be assessed before each exercise session by measuring blood pressure and asking participants if they have had any symptoms of health change since their last session.
- Exercise training will be personalised to each individual based on their fitness level and ability so as to promote a safe exercise training programme.

Another consideration is that participants will undergo a body composition assessment by DEXA which uses a very low dose radiation. Participants will be advised that this scan allows

the most accurate (i.e. 'gold-standard') measurement of their body composition (e.g. fat, bone mineral density) and it is safe, with each scan eliciting a dose of radiation equivalent to a very short airplane flight (e.g. from London to Paris).

Taking a blood sample brings risks including pain, bleeding, bruising, embolism and infection. These risks are controlled by adherence to best practice. People with CLL will be very familiar with the sensations associated with venous blood sampling as blood samples are collected regularly as part of routine care.

Wearing activity monitors for prolonged periods may, in some cases, result in some minor skin irritation, but this will be minimal and good practice minimises this risk. Participants will be provided with verbal and written information on how to use the activity monitors to minimise this risk.

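### Read literally, the adverse-event definition omits controls' non-serious events and week-0 events, and no health enquiry is described for controls between Visits 2 and 3

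*Protocol*

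**What the plan says.** The Protocol's primary objective is safety and acceptability, and the first outcome listed is the incidence and severity of AEs. The section on trial period measurements refers to Table 2 for the meaning of an AE: "Any untoward medical occurrence in a participant to whom an intervention has been administered". Table 2 adds that the event need not be caused by the product. The SAE entry in the same table carries no condition about having received an intervention. It opens "A serious adverse event in the context of this trial is any untoward medical occurrence that" and goes straight to the seriousness criteria.

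The control arm section states: "Control participants will not take part in an exercise training intervention". The trial design section sets the intervention against a comparator: "compared to standard care, which comprises routine clinical monitoring". The flow chart marks Safety in every week from 0 to 17 and does not separate the arms.

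Two places describe how health changes come to light during the 16 weeks. Under exercise sessions: "A brief screening, including blood pressure measurement and review of health status, will take place before each observed session". Under risks of participating, each session includes "asking participants if they have had any symptoms of health change since their last session". The exercise arm also keeps a home exercise diary that is reviewed weekly. Both arms complete a general health questionnaire, which covers recent infections, at Visit 2 and again at Visit 3. Both wear activity monitors at weeks 2, 6, 10 and 14. Neither the questionnaire nor the monitor points are described as AE collection.

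**The concern.** Two separate features affect the same outcome. The first is the definition. A rule that counts an event only after an intervention has been given cannot count a control's non-serious event. Nor can it count an event in either arm at the baseline visit, such as one arising from the exercise test or the blood draw. The second is ascertainment. Even with a corrected definition, one arm is asked about its health before every observed session and the other is not asked between visits.

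The Protocol counts AEs regardless of cause, and it describes a formal causality assessment only for SAEs. For non-serious events, the control arm is therefore the main described means of judging how much is background illness in this population and how much comes with exercise. The trial management group uses the safety data when it recommends whether to continue, modify or stop, and there is no separate data monitoring committee. If the control count is missing or thin, the primary safety description loses much of its value. Events never asked about cannot be recovered at the analysis stage.

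**Working it through.** The Protocol gives no numerical target, test or error rate for safety, so there is no figure to reproduce. The check sets the texts side by side and counts the enquiries.

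**1. Which events Table 2 admits, read literally**

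| Event | Counted by Table 2? | Text pointing the other way |
|---|---|---|
| Non-serious, exercise arm, after training starts | Yes, as an AE | None |
| Non-serious, control arm, weeks 1 to 17 | No, no intervention given | Safety row for weeks 1 to 17; comparison with standard care |
| Non-serious, either arm, Visit 2 (week 0) | No, nothing given yet | Safety row at week 0; risks section, which says exercise tests carry a risk of injury |
| Serious, either arm | Yes, as an SAE | None |

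The AE and SAE tiers therefore cover different populations and different periods.

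**2. Scheduled enquiries between Visit 2 and Visit 3**

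- Exercise arm: 2 observed sessions per week x 16 weeks = 32 pre-session checks per participant. For 20 participants this is 20 x 32 = 640. Both figures are maxima, because attendance is itself an outcome. The weekly diary review is additional contact.
- Control arm: 0 described.
- Routine care does not reliably fill the gap. The background section says that, after the first year, "for those with stable disease, monitoring is then extended to an annual check". A stable control may have no clinic contact in the 16 weeks.
- The first health questionnaire for controls after week 0 is at week 17.

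**3. What unequal enquiry does to a comparison**

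Observed incidence = true incidence x probability that an event is captured. If the true incidence is the same in both arms, the apparent ratio is

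capture in exercise arm / capture in control arm.

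The Protocol gives neither probability. The following uses assumed values to show the mechanism and is not an estimate. It takes capture of 0.9 in the exercise arm, a true incidence of 40% and 20 participants per arm. The exercise arm then has 20 x 0.40 x 0.9 = 7.2 expected participants with an AE.

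| Assumed control capture | Expected controls with an AE | Apparent ratio |
|---|---|---|
| 0.9 (equal) | 7.2 | 1.0 |
| 0.7 | 5.6 | 0.9/0.7 = 1.29 |
| 0.5 | 4.0 | 0.9/0.5 = 1.8 |
| 0.3 | 2.4 | 0.9/0.3 = 3.0 |

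The ratio only restates the assumed capture probabilities. What it shows is the direction when the arm asked more often reports more, and that the distortion disappears when capture is equal.

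**The case against.** The strongest reply has four parts.

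- **The wording looks like a template.** Table 2 speaks of a product, which this trial does not have. The Safety row is not split by arm, and the monitoring section promises ongoing safety monitoring without limiting it to exercisers. Controls were probably meant to be covered. This stands as a reading of intent, and it rules out claiming that the trial will in practice record no control AEs. It does not remove the conflict, because Table 2 is the operative definition. The flow chart does not settle the matter either: it marks adherence and compliance in the same undivided way, and those apply only to exercisers. Nor would intent make the enquiry equal.
- **No between-arm safety test is planned.** Safety is reported descriptively, and the Protocol asks whether events occur and whether they are unexpected and related to the trial treatment. This stands. The harm is a biased description, not a wrong error rate, although in this pilot the description is the primary result.
- **The pre-session check is brief and serves to decide whether exercise is safe that day.** It is not described as AE collection, and 32 is a maximum. This also stands, but the check would still bring out events that nobody asks controls about.
- **Some asymmetry is unavoidable when only one arm has observed sessions.** True, but a common schedule can be added alongside the sessions.

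**Conclusion.** The definition needs correcting, and AE collection in controls needs stating. Read literally, Table 2 leaves out controls' non-serious events and week-0 events in both arms, against the Safety row, the SAE definition and the stated comparator. In addition, up to 32 checks per exercise participant stand against none described for controls between visits. Any descriptive comparison of non-serious AE incidence would be biased. The direction is probably against exercise, on the assumption that more frequent asking finds more events. The amount cannot be estimated from the documents.

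A reader might infer more than this in two ways:

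- **That the safety outcome has no valid comparator at all.** The documents do not support this. SAEs are defined without restriction and count in controls. They also depend less on repeated questioning.
- **That exercise is certain to look more harmful, by some stated factor.** The documents do not support this either. They give no capture probabilities, and no between-arm test is planned.

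**What to change.** 1. Redefine an AE as any untoward medical occurrence in any consented participant, in either arm, from the start of Visit 2 procedures to Visit 3. This brings the AE tier into line with the SAE tier and with the Safety row.
2. Give the same short AE checklist, with the same questions, to both arms at the existing monitor points (weeks 2, 6, 10 and 14) and at Visit 3. The longest recall interval becomes 4 weeks, instead of the 17 weeks from week 0 to week 17 for controls.
3. Present AE incidence by arm from this common schedule. List events found only through exercise sessions separately, with their relatedness.

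The cost is a protocol amendment and a small contact burden. The checklist is given 5 times to 40 participants, 5 x 40 = 200 brief administrations. Of these, 4 x 20 = 80 are new between-visit contacts with controls, and they can accompany the monitor hand-outs already planned. The remainder fit into existing exercise-arm contacts and Visit 3. A common checklist makes the questions equal. It cannot fully remove the effect of regular session contact on what exercisers remember, so the report should say so.

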In addition to establishing the benefits of exercise training in people with 'watch and wait' CLL, this study provides a unique methodological model to investigate the effects of exercise on neoplastic activity in humans. Given that CLL tumour cells are highly abundant in peripheral blood (>5000 cells/ul) and thus easily and relatively non-invasively accessible, and the absence of confounding therapies (e.g. anti-cancer therapy), that are typical of other cancer diagnoses, people with 'watch and wait' CLL provide a unique model to prospectively assess the short-term effects of exercise training on tumour cell mass and activity *in vivo*, and in doing so conduct mechanistic investigations to discover how regular exercise averts tumour growth in humans. A number of anti-tumour mechanisms of exercise have been proposed, including immune function, inflammation, adipose tissue and metabolic hormones (McTiernan, 2008), which will be explored as secondary outcome measures in our study herein.

Accordingly, this study aims to confirm the safety and acceptability of an exercise programme in people with 'watch and wait' CLL, as well as preliminarily explore the effects of exercise training (pre-intervention to post-intervention) on tumour cell mass (CLL tumour cell frequency) in peripheral blood. The aforementioned data will be used as preliminary data for a power calculation, for a future larger randomised control trial. Additionally, this study will enable preliminary assessment of changes (pre-intervention to post-intervention) to a wide range of health outcomes in people with 'watch and wait' CLL, including cardiorespiratory fitness, strength, body composition, free-living physical activity levels, and wellbeing and physical function indices. Finally, this study will enable preliminary assessment of the changes (pre-intervention to post-intervention) to the potential anti-tumour mechanisms of exercise including immune function, inflammation, adipose tissue and metabolic hormones.

The hypotheses of this pilot study are as follows:

- Exercise will be safe and acceptable in people with 'watch and wait' CLL.
- Exercise will reduce the frequency of CLL tumour cells in the peripheral blood of people with 'watch and wait' CLL.
- Exercise will improve the cardiorespiratory fitness and the health and wellbeing of people with 'watch and wait' CLL.

Aims and outcomes

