A final important consideration for the research team when designing this study was the global COVID-19 pandemic. To minimise this risk, the exercise training intervention has been designed to be conducted in participants homes. Appropriate personal protective equipment (PPE) will be worn by the research team during Visit 1, Visit 2 and Visit 3 and the study will adopt the policies that the Trust is following and will begin recruiting when the host institution allows it.

COVID-19 Mitigation Strategies

Given safety and institutional directives with the COVID-19 pandemic in the UK, the research team will adhere to the below policies and procedures:

• Any team member displaying any COVID-19 symptoms (fever (38°C or higher), or sense of having a fever, cough, shortness of breath, muscle aches, sore throat, unexplained loss of taste or smell, diarrhoea, headache) must stay at home and organise for a COVID-19 test by contacting their GP.

- Participants and research team will use hand sanitiser on entry to the University
- The research team will be provided with appropriate PPE (apron, gloves and a face covering/face mask and face shield throughout study participant visits)
- The research team will change gloves and apron between every study participant contact
- The research team will thoroughly wash hands and forearms before and after the session (not just use hand sanitiser)
- All research equipment will be wiped down immediately with disinfectant spray and cloth between study participant sessions
- Where possible staff will be vaccinated, and lateral flow tests will be done.
- Only two members of the research team will enter the participants homes to deliver the exercise equipment, and they will be in the home for no more than 15 minutes.

Statistics and data analysis

Sample size

The aim is to recruit 40 participants. Assuming a recruitment rate of three to four people per month and 20% drop out, we estimate the target can be reached within a suitable time-frame of the funding period (16-18 months).

There is limited information available to enable a formal sample size calculation. This pilot trial will provide preliminary data to determine that a future RCT has promise and is not futile, and to perform a sample size calculation.

Statistical analysis plan

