Primary outcome measures do not lend themselves to statistical analysis. Safety will be reported as the incidence and severity of adverse events. Acceptability will be reported as proportions in terms of uptake, adherence, compliance and retention.

Secondary data will be tested for normality (e.g. Shapiro-Wilk) and in the event that some data are not normally distributed, the data will be log transformed. Descriptive statistics will be presented, and longitudinal differences and interaction effects will be identified using repeated-measures T-tests. These data will be used to inform sample size calculations in a future RCT. Incomplete data and missing values will be managed using an intention-to-treat approach with multiple imputation.

The project may utilise correlation analysis to establish whether any change in disease activity is associated to a number of mechanistic markers, and stepwise multiple regression will identify the extent to which a change in the mechanistic markers predict change in disease activity. Subgroup analysis may be performed, e.g. split to high vs. low responders or by presence of mediating variable(s) for further analysis.

Monitoring, audit and inspection

The University of Bath, as Sponsor, will monitor and conduct random audits on a selection of studies in its clinical research portfolio. Monitoring and auditing will be conducted in accordance with the Department of Health Research Governance Framework for Health & Social Care (April, 2005), and in accordance with the Sponsor's monitoring and audit policies and procedures.

Patient safety will be monitored on an ongoing basis by the research and healthcare team. A formal data monitoring committee will not be convened as this is a small single-centre pilot study. Instead, the research team will present an update on safety at quarterly trial management group meetings, together with the haematologist ([name] and/or [name]), the CI ([name]), and patient representative(s).

Ethical and regulatory considerations

Research Ethics Committee (REC) review

Before the start of the trial, approval will be sought from an NHS REC for the trial protocol, informed consent forms, participant information sheet and recruitment letter. Substantial amendments will require review by the NHS REC will not be implemented until the NHS REC grants favourable opinion.

Public and patient involvement

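### The protocol wrongly says its primary outcomes cannot be analysed statistically; without intervals, bare proportions cannot support its safety, acceptability and RCT conclusions

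*Protocol*

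**What the plan says.** The Statistical analysis plan subsection of the protocol opens with "Primary outcome measures do not lend themselves to statistical analysis". It then describes what will be reported instead: "Safety will be reported as the incidence and severity of adverse events", and "Acceptability will be reported as proportions in terms of uptake, adherence, compliance and retention". It mentions no interval or other measure of uncertainty for these outcomes.

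Other sections ask more of the same data. Background and Summary says "this study aims to confirm the safety and acceptability of an exercise programme in people with 'watch and wait' CLL", and its first hypothesis is "Exercise will be safe and acceptable in people with 'watch and wait' CLL". The Sample size subsection says the pilot will supply "preliminary data to determine that a future RCT has promise and is not futile, and to perform a sample size calculation".

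The target is 40 participants, 20 per arm, with no formal calculation. The only planning figures are in the Sample size subsection: "Assuming a recruitment rate of three to four people per month and 20% drop out". No adverse-event rate, and no level of uptake, adherence, compliance or retention, is named as acceptable or unacceptable.

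**The concern.** The opening sentence is contradicted by the two that follow it, because incidences and proportions are ordinary statistical quantities. The protocol's own list of outcomes gives most of them a numerator and a denominator. Retention, for instance, is completers of follow-up among those who completed baseline.

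This is more than detail left to a separate analysis plan. The protocol makes a positive statement that analysis does not suit these outcomes, and a later plan that added intervals would sit awkwardly with it.

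What is at stake is how a clean result would be read. With 20 people exercising, no serious adverse events and about 80% retained would look like confirmation of safety and acceptability. Without an interval, the reader is not told how poor the true figures could still be. The Sample size wording adds to this by naming only the favourable answer about a future RCT.

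**Working it through.** **Inputs from the protocol.** 20 per arm, 40 in total, 1:1 allocation; 20% dropout; three exercise sessions a week (two observed, one unsupervised) for 16 weeks.

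**The plan's own figure.** There is no power or precision figure to reproduce. The only checkable statement is that 40 can be recruited within 16 to 18 months at 3 to 4 per month:
- 40/4 = 10.0 months and 40/3 = 13.3 months.
- If 40 is read as completers after 20% dropout, 40/0.8 = 50, giving 12.5 to 16.7 months.

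Recruitment fits on either reading and is not in dispute.

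**Participant-level proportions, exact (Clopper-Pearson) 95% limits.** The observed counts are illustrations.

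| Illustrative result | 95% limits |
|---|---|
| 0 of 20 exercisers with a serious adverse event | 0 to 16.8% |
| 0 of 16 (20 less 20% dropout) | 0 to 20.6% |
| 16 of 20 retained, one arm | 56.3% to 94.3% |
| 32 of 40 retained, both arms | 64.4% to 90.9% |

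For zero events the upper limit has a closed form: 1 − 0.025^(1/20) = 0.168. The one-sided 95% version is 1 − 0.05^(1/20) = 0.139.

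**How often a reassuring figure appears when the truth is less so.** The true values here are assumptions, since the protocol gives none.
- P(no events in 20) = (1 − p)^20: 0.36 if p = 5%, and 0.12 if p = 10%.
- P(at least 32 of 40 retained): 0.11 if true retention is 70%, and 0.59 if it is 80%.

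**Session-level outcomes.** Adherence is the share of prescribed sessions completed: 3 × 16 = 48 per exerciser, and 48 × 20 = 960 in the arm. Take 80% as an illustration, 768 of 960.
- Treating sessions as independent, the exact interval is 77% to 82%.
- Sessions cluster within people. With design effect 1 + (48 − 1) × ICC, the half-width is 1.96 × √(0.8 × 0.2/960 × design effect).
- At an assumed ICC of 0.1 the design effect is 5.7 and the half-width about 6 points. At 0.5 they are 24.5 and about 13 points.

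An exact binomial interval on sessions would therefore be falsely narrow. Compliance compares prescribed with actual exercise in each session and is not a simple binomial count. For both outcomes the participant has to be the unit.

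**Why a target needs a stated comparison rule.** Suppose, for illustration only, that 80% retention were the target.
- If the lower 95% limit must exceed 80%, 38 of 40 are needed (37 of 40 gives a lower limit of 79.6%). P(at least 38 of 40) is 0.8% when true retention is 80%.
- If the interval need only include 80%, 27 of 40 passes (upper limit 81.4%).

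The same target is almost unreachable under one rule and lenient under the other.

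**The case against.** The strongest defence is that this is a 40-person phase I pilot and that descriptive reporting is normal for feasibility outcomes. The primary objective is worded as an investigation. Serious events are assessed individually for causality and expectedness, and the trial management group reviews safety quarterly and may recommend continuing, modifying or stopping. Intervals can be calculated at reporting from data already collected. All of this is fair. No hypothesis test is needed, and the protocol does not forbid statistics altogether, since it plans descriptive incidences and proportions. It does not remove the incorrect sentence or the mismatch with the aim to confirm.

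A reader might infer two stronger points that the document does not support.

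- **That no result could count against the trial's hypothesis.** The section on trial period measurements says what will be judged: recruitment, engagement, whether the intensities are achieved, and whether adverse events are unexpected and related. What is absent is a numerical criterion, not any basis for an unfavourable judgement.
- **That the pilot's observed effect will set the RCT's size or decide whether it goes ahead.** The protocol says only that the data will feed or inform a sample size calculation, which is compatible with taking just a standard deviation. Attempts to size the harm also rest on outside inputs. With 16 completers per arm, an assumed true effect of 0.5 SD and no use of baseline, the standard error is √(2/16) = 0.354 and the chance of a wrong-signed estimate is 8%. With baseline adjustment at assumed correlations of 0.5, 0.7 and 0.8 it falls to 5%, 2% and 1%. This supports a precaution, not a finding of error.

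Nor should the recruitment rate and dropout figure be read as success criteria; they are planning assumptions.

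**Conclusion.** The point holds in this form: the statement about the primary outcomes is incorrect, and reporting them without uncertainty leaves the plan unable to support its aim to confirm safety and acceptability or its conclusion about a future RCT. The size follows directly from 20 per arm: an upper limit of 16.8% on risk after no events in 20, and limits of 64% to 91% around 80% retention in 40. These intervals assume independent participants and the illustrative counts shown. The adherence half-widths of about 6 to 13 points also assume an ICC of 0.1 to 0.5, which the protocol does not give. Trial conduct is unaffected. The correction should be made before results are seen, because the wording of the safety conclusion and any targets carry weight only if fixed in advance.

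**What to change.** 1. Replace the opening sentence of the Statistical analysis plan subsection with: *Uptake, retention and the proportion of participants with an AE or SAE will be reported (by arm where applicable) with exact 95% CIs; adherence and compliance will be summarised per participant, with 95% CIs that treat the participant, not the session, as the unit (e.g. t-based or bootstrap).*
2. In the Sample size subsection, change the verb phrase from determining that an RCT has promise to informing whether it does. Limit the safety conclusion to what the upper confidence limit excludes.
3. State that the pilot's observed effect will not serve as evidence of promise or futility, nor as the RCT's target difference. Take the standard deviation, baseline correlation and attrition from the pilot.
4. If progression targets are wanted, the sponsor should set them before results are seen and state for each whether the point estimate or a confidence limit is compared with the target.

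The cost is a protocol wording amendment and conclusions stated slightly less favourably. Adding progression targets would also need a sponsor decision. No additional data are required.
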